3.3.2 Inclusion criteria

For inclusion in the study treatment period patients must fulfil all of the following criteria:

- 1. Be willing and able to comply with study procedures and provide written informed consent
- 2. Be male or post-menopausal (for more than 12 months)/surgically sterile female between 40 and 80 years
- 3. Have a clinical diagnosis of COPD
- 4. Smokers or ex-smokers (with at least 10 pack years)
- 5. Post-bronchodilator FEV₁ 30 80% predicted, FEV₁/FVC ratio < 70%

For inclusion in this genetic research, patients must fulfil the following criterion:

1. Provision of informed consent for genetic research

If a patient declines to participate in the genetic research, there will be no penalty or loss of benefit to the patient. The patient will not be excluded from other aspects of the study described in this Clinical Study Protocol, providing consent has been obtained.

3.3.3 Exclusion criteria

Any of the following is regarded as a criterion for exclusion from the study:

- 1. Concomitant diagnosis of significant pulmonary disease other than COPD, including symptomatic asthma, cystic fibrosis and allergic bronchopulmonary aspergillosis
- 2. An acute exacerbation (defined as an increase in respiratory symptoms requiring hospitalisation and/or a course of oral glucocorticosteroids and/or antibiotics, either prescribed or self administered); or acute respiratory infection (upper or lower) in the 4 weeks prior to Visit 1 or Visit 2
- 3. Use of oral corticosteroids in the 8 weeks prior to Visit 2 (use of inhaled corticosteroids is allowed)
- 4. Use of antibiotics, systemically or nebulised, in the 4 weeks prior to Visit 1 or Visit 2
- 5. Current requirement for oxygen therapy
- 6. Any other clinical disease or disorder (including insulin-dependent diabetes) which, in the opinion of the investigator, may either put the patient at risk because of participation in the study, or may influence the results of the study, or the patient's ability to participate in the study
- 7. Positive test result for HIV, Hepatitis B or C
- 8. Scheduled in-patient surgery or hospitalisation during the course of the study
- 9. Previous randomisation into the present study
- 10. Participation in another clinical study involving an investigational product within 4 weeks or 5 times the half life, whichever is longer, of Visit 1
- 11. A past history of or current clinical or laboratory evidence of renal disease, or a calculated creatinine clearance (Cockcroft-Gault formula) of \leq 70 ml/min at Visit 1
- 12. $QT_c > 450$ msec or the presence of any arrhythmia in the ECG at Visit 1. (Premature ventricular or supraventricular ectopics up to 15/minute will be allowed as long as there are no other associated cardiac abnormalities).
- 13. Any clinically relevant abnormal findings in physical examination, clinical chemistry, haematology, urinalysis, vital signs, ECG or lung function at Visit 1, which, in the opinion of the investigator, may either put the patient at risk because of participation in the study, or may influence the results of the study, or the patient's ability to participate in the study.

- 14. Patients who, in the opinion of the investigator, should not participate in the study.
- 15. History of excessive alcohol consumption or chronic alcohol induced disease
- 16. If participation in the study would result in the volunteer donating more than 1350 mL of blood in the 12 months or 500 mL of blood in the 3 months before the end of the study
- 17. The patient is not able to understand and comply with protocol requirements, instructions and protocol-stated restriction
- 18. Vulnerable patients (e.g. persons kept in detention).
- 19. Involvement in the planning and conduct of the study (applies to both AstraZeneca staff or staff at the study site)

3.3.4 Restrictions

- 1. Patients should not use oral steroids or change their inhaled corticosteroids or dosage throughout the study, unless directed by the investigator
- 2. Patients should withhold the use of short acting bronchodilators for 4 hours, and long acting bronchodilators for 12 hours prior to lung function assessments.
- 3. Use of disallowed concomitant medication (refer to Section 3.7).
- 4. Patients should not donate blood at any time during the study or for 3 months following completion of the study
- 5. Fast from the midnight (24:00) prior to dosing until 2 hours post-dose on PK sampling days, i.e. Days 1, 7 ±1 and 14. Water is allowed up to 1 hour before drug administration and will be allowed from 2 hours after drug administration
- 6. Abstain from alcohol for 72 hours prior to blood and urine samples are taken at the screening and post study medical visits. Patients will also be required to abstain from alcohol for 72 hours prior to each visit in the CPRU during each study visit.
- 7. Abstain from taking part in any other study, whilst participating in this study.
- 8. Male patients should abstain from unprotected sex and sperm donation from date of consent until 4 months after last dosing. Recommended contraception will be double barrier method, i.e. condom and in addition, the female partner to use a reliable contraceptive method, or they must refrain from sexual intercourse during the entire clinical study.
- 9. There is no evidence from clinical experience to date that AZD9668 is capable of inducing photosensitivity. However until further studies are concluded, patients

should be advised not to sunbathe or use sunbeds or U-V lamps, and to limit exposure to sunlight as much as practicable during dosing and for 1 week after last dose of study medication.

3.3.5 Discontinuation of patients from treatment or assessment

3.3.5.1 Criteria for discontinuation

Patients may be discontinued from study treatment and assessments at any time at the discretion of the Investigator. The following could be specific reasons for discontinuing a patient from the study.

- Voluntary discontinuation by the patient who is at any time free to discontinue his/her participation in the study, without prejudice to further treatment
- Safety reasons as judged by the investigator and/or AstraZeneca
- Severe non-compliance to protocol as judged by the investigator and/or AstraZeneca
- Incorrect enrolment, i.e. the patient does not meet the required inclusion/exclusion criteria for the study
- Patient lost to follow-up
- Disease exacerbation, defined as an increase in respiratory symptoms requiring hospitalisation and/or a course of oral corticosteroids and/or antibiotics (either prescribed or self administered). Patients are advised to contact the investigator if they experience an increase in respiratory symptoms for 2 consecutive days, and where possible, prior to commencing on a course of corticosteroids or antibiotics.
- An ALT / AST level ≥ 3xULN confirmed by a repeat test, or any pattern of liver function test (LFT) abnormalities giving Investigator or AZ cause for concern
- Evidence of haemolysis as evidenced by the following:
 - Reticulocyte count of over 5%, and

At least two of the following:

- a drop in haemoglobin below 10.5 g/dl
- decrease of 25% in haptoglobin. (The value post-dose to be compared with the average of two pre-dose values. The value should also be 15% below LLN).
- increase of 25% in unconjugated bilirubin or lactate dehydrogenase (LDH).
 (The value post-dose to be compared with the average of two pre-dose values. The value should also be 15% above ULN).

• A platelet count of below 80 x 10⁹/L confirmed by a repeat test (in the absence of obvious platelet clumping in a peripheral blood film).

Specific reasons for discontinuing a patient from the genetic research are:

• Withdrawal of consent for genetics research. A patient may withdraw from this genetic research at any time, independent of any decision concerning participation in other aspects of the main study described in this protocol. Voluntary discontinuation by the patient will not prejudice further treatment.

Stopping criteria for the whole study

- Two or more patients on active treatment are discontinued because of either an ALT/AST level ≥3 x ULN or any pattern of LFT abnormalities giving cause for concern
- Two or more patients on active treatment are discontinued because of evidence of haemolysis.
- Two or more patients on active treatment are discontinued because of a platelet count of below $80 \ge 10^9$ /L.

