Visit 4: End of Treatment (Days 14 & 15 ±1 day): Patients will attend the CPU with their BronkoTest[®] diary card and study medication on the morning of Day 14 in fasted state, having fasted from midnight (water will be allowed for thirst up until 1 hour before dosing) and having withheld taking their morning dose of study medication, and stay until the morning of Day 15. Blood will also be collected pre-dose for assessment of PK, hsCRP and serum amyloid A. Before administration of the morning dose on Day 14, safety assessments (vital signs, ECG, lung function, haematology, clinical chemistry, urinalysis and urine drug screen) will be performed. Patients will then take their morning dose of study medication in the CPU. This will be the final dose of study medication. At 1 hour post-dose, an ECG will be recorded. Approximately 1-2 hours after this last dose, patients will provide an induced sputum sample (around the same time they had the induced sample on Day -1); weight of the sample will be recorded, and the sample processed for neutrophils and AZD9668 levels.

All urine produced over the 24 hours after the last dose will be collected for measurement of desmosine levels and AZD9668 concentrations. Urine will be collected for time periods 0-4 hours, 4-12 hours and 12-24 hours. Aliquots from each of these collections will be taken for urine PK, and an aliquot from the pooled sample will be taken for urine desmosine. Serial blood samples will be collected for PK analysis at pre-dose and at 0.25, 0.5, 1, 2, 3, 4, 5, 6, 8, 12, and 24 hours post dose. On the morning of Day 15, a spontaneous sputum sample will be collected for quantitative bacteriology, and the patients will be discharged from the CPU with their BronkoTest[®] diary card to bring to their follow-up visit.

Visit 5: Follow-up (Day 21 ±3 days): Patients will return to the CPU with their BronkoTest[®] diary card in fasted state, having fasted from midnight (water allowed), for follow-up safety assessments (physical examination, vital signs, ECG, lung function, haematology, clinical

chemistry and urinalysis). A blood sample for hsCRP and serum amyloid A will also be collected at this visit.

Throughout the study, lung function measurements should be performed at the same time of day ± 2 hours in relation to the time point at Visit 1 (baseline).

Each patient will attend the visits as outlined in Figure 1.

[figure not shown]

Table 1Study plan

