3.4.2 Doses and treatment regimens

In the current study the daily dose will be 120 mg (i.e. 60 mg b.i.d), except for days 1 and 14 when patients will receive only the morning dose to allow assessment of PK. This dose has been chosen as a dose that is predicted to achieve trough steady state therapeutic plasma concentrations of 19 nM (predicted from an in vivo mouse acute lung injury model) in all patients, whilst ensuring that the predicted geometric mean $C_{max,ss}$ and $AUC_{(0-24)ss}$ are below the HELC limits. The estimated margins to the HELC limits are 2.6 and 1.4 for $C_{max,ss}$ and $AUC_{(0-24)ss}$, respectively, in the fasted state. If a dose of 60 mg b.i.d is not tolerated by an individual patient then his/her dose may be halved to 30 mg b.i.d for the remainder of the study, at the investigator's discretion. The population PK model predicts that this will still achieve trough steady state plasma concentrations above 19 nM in all patients.

For morning doses administered on Days 1, 7 and 14, patients will be fasted from midnight the night before dosing except water for thirst. The patients may consume water up to 1 hour before dosing. The dose will be administered with 240 mL of water, and the patients must drink all the water. The patients must not consume any further fluids or food for a minimum of 2 hours post dose. At this time the patients will be allowed a light breakfast. Fasting the patients prior to receiving their morning dose on days when they are having ECG measurements ensures that the ECG measurements can be taken when C_{max} is maximised. There is no requirement to restrict food consumption before or immediately after administration of the remaining doses. These doses can be administered with approximately 100 mL water.

The morning and evening doses will be filled individually in high-density polyethylene (HDPE) bottles with a child resistant cap according to the random scheme. All bottles for morning and evening dose for 14 days will be packed in a white box for each patient.

At Visit 2, the required number of bottles needed for the morning and evening dose until Visit 3 will be handed over to the patient after the 4th dose has been taken in the CPU.

At Visit 3, the required number of bottles until Visit 4 will be handed over to the patient after the morning dose has been administered.

At Visit 4, the patient will be administered the morning dose in the CPU by the staff.

[figure not shown]

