OAEs will be identified by the Study Delivery Team Physician in consultation with the appropriate Global Drug Safety Physician during the evaluation of safety data for the Clinical Study Report. Significant adverse events of particular clinical importance, other than SAEs and those AEs leading to discontinuation of the patient from study treatment, will be classified as OAEs. Examples of these are marked haematological and other laboratory abnormalities, and certain events that lead to intervention (other than those already classified as serious), dose reduction or significant additional treatment. For each OAE, a narrative may be written and included in the Clinical Study Report.

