- Evidence of haemolysis as evidenced by the following:
 - Reticulocyte count of over 5%, and

At least two of the following:

- a drop in haemoglobin below 10.5 g/dl
- decrease of 25% in haptoglobin. (The value post-dose to be compared with the average of two pre-dose values. The value should also be 15% below LLN).
- increase of 25% in unconjugated bilirubin or lactate dehydrogenase (LDH).
 (The value post-dose to be compared with the average of two pre-dose values. The value should also be 15% above ULN)
- A platelet count of below $80 \ge 10^9$ /L confirmed by a repeat test (in the absence of obvious platelet clumping in a peripheral blood film).
- A QTcF >500 ms on active treatment (QT interval corrected for heart rate by Fridericia method) or a QTcF prolongation >60 ms on average compared to baseline, confirmed by a repeat ECG in 30 minutes.

Section of protocol affected:

3.3.5, Discontinuation of patients from treatment or assessment3.3.5.1, Criteria for discontinuation, Stopping criteria for the whole study, page 30

Previous text:

Stopping criteria for the whole study

- Two or more patients on active treatment are discontinued because of either an ALT/AST level ≥3 x ULN or any pattern of LFT abnormalities giving cause for concern
- Two or more patients on active treatment are discontinued because of evidence of haemolysis
- Two or more patients on active treatment are discontinued because of a platelet count of below $80 \times 10^9/L$

Revised text:

Stopping criteria for the whole study

- Two or more patients on active treatment are discontinued because of either an ALT/AST level ≥3 x ULN or any pattern of LFT abnormalities giving cause for concern
- Two or more patients on active treatment are discontinued because of evidence of haemolysis
- Two or more patients on active treatment are discontinued because of a platelet count of below $80 \ge 10^9/L$
- A QTcF >500 ms on active treatment (QT interval corrected for heart rate by Fridericia method) or a QTcF prolongation >60 ms on average compared to baseline, confirmed by a repeat ECG in 30 minutes in 2 or more subjects on active treatment

Section of protocol affected:

Section 10, References, page 58

Added reference:

GOLD 2007

Global Initiative for Chronic Obstructive Lung Disease. Global Strategy for the Diagnosis, Management, and Prevention of Chronic Obstructive Pulmonary Disease. Updated 2007. http://www.goldcopd.org

Reason for Amendment:

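### The liver, haemolysis and platelet study-stop rules count discontinuations, so two active patients can meet a criterion without the stop being reached

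*Protocol*

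**What the plan says.** Section 3.3.5.1 lists criteria for taking an individual patient off the study and then gives stopping criteria for the whole study.

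- **Whole-study rules.** The haemolysis rule is "Two or more patients on active treatment are discontinued because of evidence of haemolysis". The liver and platelet rules are built the same way: two or more active patients discontinued for that finding. Amendment 01 reissued the list with these three rules unchanged.
- **Added QTcF rule.** Amendment 01 adds a rule for QTcF above 500 ms, or prolonged by more than 60 ms, "confirmed by a repeat ECG in 30 minutes in 2 or more subjects on active treatment". It sets no condition that the subjects were discontinued.
- **Patient-level action.** The section opens with "Patients may be discontinued from study treatment and assessments at any time at the discretion of the Investigator" and introduces its list with "The following could be specific reasons for discontinuing a patient from the study". Amendment 01 keeps both sentences.
- **Timing.** On the Day 14 morning dose, Section 3.1 says "This will be the final dose of study medication". Table 1, note c, schedules safety bloods before the morning dose on Days 2, 7 and 14, and again at follow-up (Visit 5).

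**The concern.** A study-level safety stop should respond to the finding. These three rules respond to an action that may or may not follow it. A patient can meet a limit and go uncounted in two ways: the investigator may use the discretion in Section 3.3.5.1 and keep the patient on drug, or the result may first appear when treatment is already over.

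The rules carry some weight in this trial. Sections 6.6 and 6.7 provide for no interim analysis and no data monitoring board. Section 1.1 reports minor haematological abnormalities at high doses in the 28-day dog study, and Section 3.2.2 says such abnormalities will continue to be monitored. Earlier multiple dosing in man lasted 8 days; here it lasts 14. At stake is whether patients still being dosed, or not yet enrolled, are protected once two active patients have crossed the same limit.

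**Working it through.** The Protocol states no figure for these rules, so there is none to reproduce. The check rests on the wording and the schedule.

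**1. What each provision counts**

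| Provision | Place | What is counted | Consequence |
|---|---|---|---|
| Liver, haemolysis and platelet stops | 3.3.5.1; repeated in Amendment 01 | Active patients discontinued for the finding | Study stops |
| QTcF stop | Amendment 01 | Active subjects with the confirmed finding | Study stops |
| Unblinding | 3.6.2 | Patients who meet the discontinuation criteria | Codes may be opened |
| Adverse event recording | 4.7.1.2 | Any laboratory abnormality meeting the criteria | Recorded as an adverse event |

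Only the three laboratory stops depend on discontinuation. No sentence makes discontinuation automatic once a criterion is met.

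**2. Timing of the safety bloods against dosing (nominal days)**

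Total doses: Day 1 = 1; Days 2 to 13 = 12 × 2 = 24; Day 14 = 1; sum = 26.

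| Draw | Doses already taken |
|---|---|
| Day 2, pre-dose | 1 |
| Day 7, pre-dose | 1 + 5 × 2 = 11 |
| Day 14, pre-dose | 1 + 12 × 2 = 25 |
| Visit 5 | 26 |

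Gap from last dose to Visit 5: nominally 21 − 14 = 7 days; shortest under the visit windows 18 − 15 = 3; longest 24 − 13 = 11.

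Visit 5 is both after treatment and the last scheduled assessment, so a first-onset result there leaves nothing to discontinue. A Day 14 result could raise the same difficulty if it, or the repeat required for ALT/AST and platelets, comes back after that morning's dose. The Protocol does not state turnaround time.

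**3. Illustration only**

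Let p be the chance that an active patient meets a given criterion, and q the chance that such a patient is discontinued for it. The Protocol gives neither, so both are assumptions, as is independence between patients. With 18 × 2/3 = 12 active patients, the chance that the rule triggers is P(X ≥ 2), where X is binomial (12, p × q).

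| Assumed p | q = 1 | q = 0.75 | q = 0.5 | q = 0.25 |
|---|---|---|---|---|
| 0.05 | 0.118 | 0.072 | 0.035 | 0.009 |
| 0.10 | 0.341 | 0.226 | 0.118 | 0.035 |
| 0.20 | 0.725 | 0.557 | 0.341 | 0.118 |

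Given exactly two qualifying active patients, the rule triggers with probability q²: 1.00, 0.56, 0.25 and 0.06 at the same four values of q. Counting patients who meet the criterion corresponds to q = 1. The table shows how the rule depends on q; it does not estimate the chance of a missed stop.

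**The case against.** The strongest reply is that the Protocol does respond to patients who meet a criterion. Section 3.6.2 allows codes to be opened, after consultation with the sponsor's drug safety physician, once two or more patients meet the discontinuation criteria, with no requirement that they were discontinued and no end-of-treatment limit. Section 4.7.1.2 requires a laboratory abnormality that meets the stopping criteria to be recorded as an adverse event, with recording through Visit 5. (Section 4.7.2.3 gives a narrower general reporting rule, but 4.7.1.2 addresses these criteria specifically.) The sponsor as well as the investigator may judge that a patient should stop for safety, and many investigators would discontinue such a patient anyway. Counting discontinuations also ties the study stop to cases judged serious enough to act on. All of this stands and limits the practical effect. What it does not supply is a stop: the unblinding step is optional and leads to no stated action on the study.

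Three stronger readings are not supported:

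- A reader might infer from Section 3.4.2, where "his/her dose may be halved to 30 mg b.i.d for the remainder of the study", that patients over a laboratory limit would be kept on a reduced dose. That provision concerns a dose that is not tolerated and is not linked to these thresholds.
- A reader might infer the same from the definition of other significant adverse events in Section 4.7.1.1 ("Examples of these are marked haematological and other laboratory abnormalities"). That is a classification made for the study report, and a marked abnormality may fall short of the limits in Section 3.3.5.1.
- A reader might take one post-treatment draw out of four as the share of cases missed. It is a share of visits and says nothing about when abnormalities arise. The Day 14 draw already follows 25 of the 26 doses.

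**Conclusion.** The point holds as a minor defect of wording. As written, two active patients can meet the same ALT/AST, haemolysis or platelet criterion without the study stop being reached, because discontinuation is discretionary and cannot follow a first-onset result at Visit 5. The QTcF rule in the same list does not share the weakness.

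The conclusion rests on the text of Section 3.3.5.1, Amendment 01 and the visit schedule, not on assumed rates. Its practical size is unknown: the Protocol gives no incidence for these findings, no rate of discontinuation among those who meet a criterion, and no enrolment pace. A stop helps only if other patients are still being dosed or have yet to enrol. The documents do not support saying that qualifying patients would be kept on drug, or that such cases would go unrecorded. No estimate or planned analysis is affected.

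**What to change.** Reword the three laboratory bullets so that each counts two or more patients who received AZD9668 and meet the ALT/AST, haemolysis or platelet criterion of Section 3.3.5.1 at any post-dose assessment through Visit 5, whether or not they were discontinued. Keep confirmation by repeat test where the criterion already requires it, and allow that repeat to follow Visit 5 when the first abnormal result appears there. Counting by treatment received matches the safety analysis set in Section 6.3. The liver limb that covers any worrying pattern of liver tests has no numeric limit and should stay a judgement.

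Thresholds and the count of two do not change, and no scheduled samples are added. The cost is a change to three bullets in the next amendment and a somewhat higher chance that a rule triggers, possibly on cases the investigator thought compatible with continuing. Under the illustrative assumptions p = 0.10 and q = 0.75, the chance of triggering rises from 0.226 to 0.341.
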